14.0 Body Fluid Specimens

None

15.0 Drug Information

15.1 Pembrolizumab (MK-3475, SCH 900475, Keytruda®)

15.11 **Background:** Pembrolizumab is a potent humanized IgG4 monoclonal antibody with high specificity of binding to the PD-1 receptor, thus inhibiting its interaction with PD-L1 and PD-L2. Based on preclinical *in vitro* data, pembrolizumab has high affinity and potent receptor blocking activity for PD-1.

15.12 Formulation

Pembrolizumab is available as a liquid 25 mg/mL, 100 mg/vial.

15.13 Preparation and storage:

Vials should be stored in the refrigerator at temperatures between 2-8°C. Drug concentrate is further diluted with normal saline (or 5% dextrose in the concentration range of 1 to 10 mg/mL) in IV containers made of polyvinyl chloride (PVC) or non-PVC material. The infusion solution in the IV bag should be immediately administered. Pembrolizumab solutions may be stored at room temperature for a cumulative period of up to 4 hours. This includes room temperature storage of reconstituted solution in vials, room temperature storage of infusion solution in the IV bag and the duration of infusion.

In addition, IV bags may be stored at 2-8 °C for up to a cumulative time of 20 hours. If refrigerated, the vials and/or IV bags should be allowed to equilibrate to room temperature prior to subsequent use.

15.14 **Administration:** Pembrolizumab is administered by intravenous infusion over 30 minutes via a 0.22 micron in-line filter. The final infusion volume must be between 1 and 10 mg/mL. Maximum rate of infusion should not exceed 6.7 mL/minute through a peripheral or indwelling catheter. Flush the line with 0.9% NaCL following the completion of the infusion.

15.15 Pharmacokinetic information:

a) Absorption – during repeated dosing of MK-3475 every two weeks, steady state conditions were reached within 16 weeks of treatment. Steady state trough concentrations obtained at 24, 36 and 48-weeks of treatment

with 10 mg/kg Q2W were on average 20% percent higher compared to 10 mg/kg Q3W treatment.

b) Distribution – pembrolizumab has a limited volume of distribution.

c) Excretion – mean estimated $t_{1/2}$ values from the 28-day single dose profiles ranged from 14.1 to 21.6 days. Clearance is nonlinear and saturable.

15.16 **Potential Drug Interactions:** There are no known significant drug interactions.

15.17 **Known potential toxicities:**

Common known potential toxicities, >10%:

Cardiovascular: Peripheral edema

Central nervous system: Fatigue, headache, chills, insomnia, dizziness

Dermatologic: Pruritus, skin rash, vitiligo

Endocrine & metabolic: Hyperglycemia, hyponatremia, hypoalbuminemia, hypertriglyceridemia, hypocalcemia

Gastrointestinal: Nausea, decreased appetite, constipation, diarrhea, vomiting, abdominal pain

Hematologic & oncologic: Anemia

Hepatic: Increased serum AST

Neuromuscular & skeletal: Arthralgia, limb pain, myalgia, back pain

Respiratory: Cough, dyspnea, upper respiratory tract infection

Miscellaneous: Fever

Less common known potential toxicities, 1% - 10%:

Dermatologic: Cellulitis

Endocrine & metabolic: Hypothyroidism, hyperthyroidism

Gastrointestinal: Colitis

Infection: Sepsis

Renal: Renal Failure

Respiratory: Pneumonitis, pneumonia

Rare known potential toxicities, <1% (Limited to important or life-threatening):

Adrenocortical insufficiency (immune-mediated), arthritis (immune-mediated), exfoliative dermatitis (immune-mediated), hemolytic anemia (immune-mediated), hepatitis (including autoimmune hepatitis; grade 4: <1%), hypophysitis (grade 2: <1%; grade 4: <1%), interstitial nephritis (with renal failure; grade 3: <1%; grade 4: <1%), Lambert-Eaton syndrome (immune-mediated), myositis (immune-mediated), nephritis (grade 2 autoimmune: <1%), optic neuritis (immune-mediated), pancreatitis (immune-mediated), partial epilepsy (immune-mediated; in a patient with inflammatory foci in brain parenchyma), rhabdomyolysis (immune-mediated), uveitis (immune-mediated)

15.18 **Drug procurement:** Pembrolizumab will be provided free of charge to study participants by Merck.

15.19 **Nursing Guidelines:**

15.191 Pembrolizumab side effects vary greatly from those of traditional chemotherapy and can vary in severity from mild to life threatening.

Instruct patients to report any side effects to the study team immediately. Side effects may be immediate or delayed up to months after discontinuation of therapy. Most side effects are reversible with prompt intervention of corticosteroids.

- 15.192 Diarrhea can be seen however, is less common than that seen with anti-CTLA-4 agents. However it can be severe, leading to colonic perforation. Instruct patients to report ANY increase in the number of stools and/or change in baseline, blood in the stool, abdominal pain to the study team immediately.
- 15.193 Rash/pruritis/dermatitis is seen. Patients should report any rash to the study team. Treat per [Section 9.0](#) and monitor for effectiveness.
- 15.194 Monitor LFT's closely as elevations in these levels could indicate early onset autoimmune hepatitis. Patients should also be instructed to report any jaundice, or right upper quadrant pain to the study team immediately.
- 15.195 Pneumonitis can be seen and may be mild (only seen on imaging) to severe. Patients should be instructed to report any SOB, dyspnea, cough, chest pain, etc. to the study team immediately. Patients reporting these symptoms should have a pulse ox checked and consider immediate imaging per the treating MD.
- 15.196 Endocrinopathies (including hypopituitarism, hypothyroidism, hypophysitis, and adrenal insufficiency) are seen with this agent. Patients may present only with the vague sense of fatigue and "not feeling well." Additional symptoms may be that of nausea, sweating and decreased activity tolerance. Instruct patients to report these signs or symptoms immediately and obtain appropriate labs as ordered by MD.
- 15.197 Patients who are started on steroid therapy for any side effects of pembrolizumab toxicity should be instructed to take the steroids as ordered, and not to discontinue abruptly as symptoms may return and be severe. Patients may be on steroid therapy for weeks. Instruct patients to report any increase or change in side effects with any dosage decrease as patients may need a slower taper.
- 15.198 Fatigue is common and may or may not be associated with immune related side effects. Assess patient's fatigue level prior to each cycle of therapy and report any changes to the study team.
- 15.199 Patients should avoid receiving live vaccines within 30 days of study drug administration or per other study guidelines.
- 15.200 Patients who have undergone an allogenic bone marrow transplant, have an increased risk of severe complications including early GVHD, and venoocclusive disease, if they have previously been treated with pembrolizumab.

- 15.201 Myocarditis has been reported and associated with pembrolizumab. Instruct patients to report chest pain, SOB, or dyspnea to study team immediately and/or seek emergency medical attention.
- 15.202 Autoimmune hematologic disorders including ITP and hemolytic anemia have been reported. Monitor blood counts closely and report any abnormalities to the study team.
- 15.203 Rare neurologic disorders including Guillian-Barre syndrome and myasthenia gravis have been reported. Instruct patients to report any neurologic symptoms including weakness, parasthesias, or numbness, tingling to the study team immediately.

15.2 Imiquimod

15.21 **Preparation and Storage:**

Single-use, 0.25 gm packets, containing 5% imiquimod. This is a commercial product that will be dispensed from the pharmacy. One or two packets will be used for each application.

15.22 **Known Potential Toxicities:**

Local Reactions:

Local skin reactions have been reported with imiquimod as used for genital warts. Erythema, excoriation/flaking, and edema are described as “common” in the package insert. Itching, burning, pain, and soreness occur at the treatment site. Remote skin reactions can occur in less than 5% of patients. Ulceration, scabbing, and vesicles occur in 3 to 5%. Fungal infections are reported in 11% of women using imiquimod. The vaginal and cervical tissues are likely to be at least as sensitive to the inflammatory effects as the vulvar tissues. Examination prior to each application will be the primary means of protecting patients from cumulative local toxicities.

Systemic Reactions:

Systemic reactions have not been a major problem with topical use of imiquimod. When systemic symptoms are reported, they are suggestive of a viral syndrome. Headaches, myalgias, and flu-like symptoms have been reported. The frequency of these symptoms with vulvar application appears to be elevated no more than 1% over the frequency in the placebo group. The frequency of systemic symptoms with repeated application will be monitored in this trial.

15.23 Nursing guidelines:

15.231 Patients should wear gloves (if possible) while applying imiquimod. Instruct patient to wash hands carefully when done.

15.232 Avoid contact with eyes and mucous membranes.

15.233 A certain amount of redness, irritation, and/or burning is expected at the site of administration. Patients experiencing large areas of erythema or significant pain with administration should be instructed to call the study team immediately.

15.234 Rarely if patients are applying to large surface areas, they can experience mild flu-like symptoms (i.e myalgias, fatigue, etc). Instruct patient to report these to the study team. Treat symptomatically and monitor for effectiveness.

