10.6 Required Routine Reporting

10.61 Baseline and Adverse Events Evaluations

Pretreatment symptoms/conditions to be graded at baseline and adverse events to be graded at each evaluation per CTCAE v4.0 grading **unless** otherwise stated in the table below:

System Organ Class (SOC)	Adverse event/Symptoms	Baseline	Each evaluation
Blood and lymphatic system disorders	Anemia	X	X
	Febrile Neutropenia		X
Cardiac Disorders	Myocardial infarction		X
Gastrointestinal disorders	Nausea	X	X
	Vomiting	X	X
	Abdominal pain	X	X
	Baseline # of stools	X	

	Diarrhea		X
General disorders and administration site conditions	Fatigue	X	X
	Fever		X
Immune system disorders	Allergic reaction		X
	Anaphylaxis		X
Investigations	Neutrophil count decreased		X
	Platelet count decreased		X
	White blood cell decreased		X
	Aspartate aminotransferase increased	X	X
	Alkaline phosphatase increased	X	X
	Blood bilirubin increased	X	X
Musculoskeletal and connective tissue disorders	Arthralgia	X	X
	Myalgia	X	X
Nervous system disorders	Peripheral sensory neuropathy	X	X

10.62 Submit via appropriate MCCC Case Report Forms (i.e., paper or electronic, as applicable) the following AEs experienced by a patient and not specified in Section 10.6:

10.621 Grade 2 AEs deemed *possibly, probably, or definitely* related to the study treatment or procedure.

10.622 Grade 3 and 4 AEs regardless of attribution to the study treatment or procedure.

10.623 Grade 5 AEs (Deaths)

10.6231 Any death within 30 days of the patient's last study treatment or procedure regardless of attribution to the study treatment or procedure.

10.6232 Any death more than 30 days after the patient's last study treatment or procedure that is felt to be at least possibly treatment related must also be submitted as a Grade 5 AE, with a CTCAE type and attribution assigned.

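### Grade 1 headache and grade 1 application-site reactions have no clear route to the case report form, although the protocol says systemic symptoms will be monitored and cutaneous irritation routinely reported

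*Combined protocol and SAP*

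**What the plan says.** Section 2.1 makes the safety profile of the combination part of the primary goal. Section 15.22 describes the systemic effects of imiquimod: "Headaches, myalgias, and flu-like symptoms have been reported". It then commits the trial: "The frequency of systemic symptoms with repeated application will be monitored in this trial".

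Routine collection has two parts. Section 10.61 gives a list of terms with the instruction "Pretreatment symptoms/conditions to be graded at baseline and adverse events to be graded at each evaluation per CTCAE v4.0 grading"; no minimum grade applies to listed terms. Section 10.62 then asks for "the following AEs experienced by a patient and not specified in Section 10.6". These are "Grade 2 AEs deemed *possibly, probably, or definitely* related to the study treatment or procedure", grade 3 and 4 events whatever the attribution, and deaths.

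Section 10.32 exempts fatigue, malaise and imiquimod skin irritation, each up to grade 3, from expedited reporting, but requires that they still be reported routinely and points to Section 10.6. Section 16.31 plans one safety summary: for each reported toxicity, the proportion of patients with a severe level.

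**The concern.** The protocol expects imiquimod's effects to be mostly mild. Section 15.233 expects some redness, irritation or burning, 15.22 calls erythema, flaking and edema common, and 15.234 says of patients treating large areas that "they can experience mild flu-like symptoms". A collection rule that starts at related grade 2 for unlisted terms misses that range for any symptom without its own row.

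In a 10-patient single-arm pilot the safety result is essentially a description. If grade 1 headache or application-site reaction is not requested prospectively, its frequency may not be recoverable later. Sites would also be working from instructions on mild skin irritation that do not agree.

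**Working it through.** No figure in the plan belongs to this point. The only computed design figure, the upper 95% bound for 0 responses in 10, reproduces as 1 − 0.05^(1/10) = 0.2589, or 25.9%, and is unaffected. The check is therefore a comparison of sections.

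**Step 1: the list.** Section 10.61 has 21 rows. Searching them for skin, rash, pruritus, erythema, headache, flu-like and malaise terms finds none. Myalgia, fatigue and fever appear once each; myalgia and fatigue are graded at baseline and each evaluation, fever at each evaluation only.

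**Step 2: each event against the collection rules in 10.6.**

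| Event | Where the protocol names it | Row in 10.61 | Grade 1 route in 10.6 |
|---|---|---|---|
| Myalgia | 15.22, 15.234 | Yes | Yes |
| Fatigue | 10.32, 15.234 | Yes | Yes |
| Headache | 15.22; 15.17 (over 10% with pembrolizumab) | No | None |
| Flu-like symptoms | 15.22, 15.234, 8.2 | No | Only through myalgia, fatigue, fever |
| Application-site reaction or irritation | 15.22, 15.233, 8.2, 10.32 | No | None |
| Malaise | 10.32 | No | None |
| Rash, pruritus | 15.17 (over 10% with pembrolizumab) | No | None |

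For the events without a row, grade 2 is collected only if attribution is at least possible; grade 3 and above is always collected.

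**Step 3: against the 15.22 commitment.** Of the three systemic symptoms named, one (myalgia) is collected at every grade, one (flu-like symptoms) in part, and one (headache) only from related grade 2.

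**Step 4: against 10.32.** Of the three events sent to routine reporting under 10.6, one (fatigue) has a row and two (malaise, skin irritation) do not. Read literally, up to grade 3 includes grade 1, which 10.62 does not request. The two sections do not agree.

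**Step 5: against the analysis.** Section 16.31 reports severe proportions and the stopping rule in 16.61 uses grade 4 events. Both are fed by 10.62, so neither loses data. However, no planned summary reports an any-grade frequency, even for listed terms, so the frequency promised in 15.22 has no matching output.

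**The case against.** The strongest reply is that the promise is largely kept. Section 15.22 commits only to systemic symptoms, not skin reactions. Myalgia is graded at any grade, and 15.234 explains flu-like illness by components that are mostly listed: "they can experience mild flu-like symptoms (i.e myalgias, fatigue, etc". This stands. A reader might infer that the mild imiquimod reactions as a group go unrecorded, or that the missing skin terms breach the 15.22 sentence; the documents support neither. Against that sentence, the gap is grade 1 headache and the absence of a flu-like term. The skin gap rests on 10.32 and the primary safety goal.

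Second, 10.32 is headed as dealing with expected serious events, so it may have been meant only for events that would otherwise be expedited, with mild irritation not in view. That is possible, but the text sets no lower grade and refers to a section with no matching row. It still needs reconciling.

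Third, a reader might infer that reactions at a tumour site have no baseline reference. They do: the Section 4.0 test schedule requires lesion photographs and a physical examination before registration and on day 1 of each cycle. Only a CTCAE baseline grade is missing.

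Fourth, no planned analysis changes. This is true of 16.31 and 16.61, and it limits the weight of the point. It does not answer the monitoring statement in 15.22 or the routing in 10.32.

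**Conclusion.** The point holds in a limited form. Followed exactly, Section 10.6 gives grade 1 headache and grade 1 application-site reaction no clear route to the case report form, and it captures flu-like illness only through its components. This falls short of 15.22, conflicts with 10.32 as written, and limits the primary safety description. Severe events are captured in full.

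The conclusion rests on reading 10.61 and 10.62 as the complete routine collection rule; the case report forms and the Data Submission Schedule are not among the documents, and rows there could already close the gap.

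It is tempting to attach a percentage to the under-count. The documents do not support one. They give no grade mix, and no frequency for weekday imiquimod on melanoma lesions with pembrolizumab. What they do say about systemic effects points to low rates: no more than 1% above placebo with vulvar application, and flu-like symptoms described as rare.

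**What to change.** - Add six terms to the 10.61 table, graded at baseline and at each evaluation: application-site skin reaction, rash, pruritus, headache, flu-like symptoms and malaise.
- Reconcile 10.32 with 10.6, so that malaise and imiquimod skin irritation have the routine row that 10.32 presupposes and the grades to be reported are stated.
- In 16.31, report any-grade proportions for these terms beside the severe proportions.
- Leave the existing rows in place. In particular, peripheral sensory neuropathy should not be removed to save space: 15.203 asks patients to report numbness and tingling, and the note to 3.29b admits patients with neuropathy up to grade 2.

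The cost is six form rows at visits that already include an adverse event assessment and photographs, so slightly more data entry. Reported any-grade rates will rise, and the report should say that these terms were solicited. No dose, visit or sample size changes.

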15.24 Drug Procurement

The research base pharmacy will obtain the drug from 3M Pharmaceuticals. Each institution will order the drug from the research base pharmacy. Submit the drug order form to:

Outdated or remaining drug is to be destroyed on-site as per procedures in place at each institution.

16.0 Statistical Considerations and Methodology

16.1 This pilot study will enroll 10 patients to gain preliminary data on the anti-tumor activity and safety profile of the combination of imiquimod and pembrolizumab in patients with unresectable cutaneous melanoma.

If there are no tumor responses documented among these 10 patients, then upper bound of a one-sided 95% confidence interval for the tumor response rate would be 25.9%.

All patients meeting the eligibility criteria who have signed a consent form and have begun treatment will be evaluable for assessment of all of the clinical endpoints.

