- 1.9c11 Clinical Efficacy Endpoint- The expected single agent response rate of pembrolizumab is ~40% in the front line setting and ~25% when given after progression on ipilimumab. Given the small number of patients to be enrolled onto this trial, we will construct a 90% confidence interval for the proportion of patients who have a CR or PR on two consecutive evaluations at least 6 weeks among all the patients enrolled on this trial.
- 1.9c12 Clinical Safety Endpoint - Given the non-overlapping toxicities of pembrolizumab and imiquimod, we expect serious toxicities to occur at a rate similar to each drug individually. For example, pembrolizumab induces serious adverse events in ~10% of patient and imiquimod induces serious adverse events in 1-3% of patients. Therefore we expect ~10-13% of patient to experience a serious adverse event.

1.9d Biomarker Research

One of the largest unmet needs in improving the therapeutic potential of pembrolizumab is identifying reliable predictive biomarkers. In this study, the biomarker research will be exploratory in nature and will include assessing total tumor RNA through RNA seq and PDL1 expression through the use of immunohistochemistry. Attempts will then be made to associate molecular markers with clinical outcomes.

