3.0 Patient Eligibility

3.1 Registration – Inclusion Criteria

- 3.11 Age \geq 18 years.
- 3.12 Histological confirmation of Stage IIIB, IIIC, IVM1a, IVM1b, or IVM1c that is not suitable for surgical resection.
- 3.13 Patients must not have received prior pembrolizumab or other anti-PD1/PDL1 therapies for their metastatic disease.

- 3.14 At least one cutaneous lesion that is amenable to treatment with topical imiquimod.
- 3.15 Measurable disease by RECIST as defined in Section 11.0.
- 3.16 ECOG Performance Status (PS) of 0 or 1 (Appendix I).
- 3.17 The following laboratory values obtained ≤ 14 days prior to registration.
- Absolute neutrophil count (ANC) $\geq 1500/\text{mm}^3$
 - Platelet count $\geq 100,000/\text{mm}^3$
 - Hemoglobin $> 9.0 \text{ g/dL}$ or $\geq 5.6 \text{ mmol/L}$ without transfusion or EPO dependency (within 7 days of assessment).
 - Serum total bilirubin $\leq 1.5 \times \text{ULN}$ or Direct bilirubin $\leq (\text{ULN})$ for subjects with total bilirubin levels $> 1.5 \text{ ULN}$
 - Aspartate transaminase (AST) $\leq 2.5 \times \text{ULN}$ or $\leq 5 \times \text{ULN}$ for subjects with liver metastases.
 - Albumin $\geq 2.5 \text{ mg/dL}$
 - Creatinine $\leq 1.5 \times$ upper limit of normal (ULN)
- NOTE:** Measured or calculated (per institutional standard) creatinine clearance is acceptable $\geq 60 \text{ mL/min}$ for subject with creatinine levels $> 1.5 \times$ institutional ULN. Calculated creatinine clearance can be used in place of creatinine or CrCl and must be $\geq 45 \text{ mL/min}$ using the Cockcroft-Gault formula below:

Cockcroft-Gault Equation:

$$\text{Creatinine clearance for males} = \frac{(140 - \text{age})(\text{weight in kg})}{(72)(\text{serum creatinine in mg/dL})}$$

$$\text{Creatinine clearance for females} = \frac{(140 - \text{age})(\text{weight in kg})(0.85)}{(72)(\text{serum creatinine in mg/dL})}$$

- 3.18 Negative urine or serum pregnancy test done ≤ 72 hours prior to first treatment, for women of childbearing potential only.

If the urine test is positive or cannot be confirmed as negative, a serum pregnancy test will be required.

- 3.19a Provide informed written consent.
- 3.19b Willing to return to enrolling institution for follow-up.
- 3.19c Willing to provide tissue from a newly obtained core or excisional biopsy of a tumor lesion in appropriate low risk cutaneous lesions.

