- 13.4 Patients who complete 2 years of protocol treatment (approximately 35 cycles) without (confirmed) disease progression will proceed to the Observation phase until confirmed disease progression or a maximum of 3 years post registration. If the patient has a documented confirmed disease progression during observation, the patient will continue on to the event monitoring phase for a maximum of 3 years post registration.
- 13.5 A patient is deemed ineligible if after registration, it is determined that at the time of registration, the patient did not satisfy each and every eligibility criteria for study entry.
- If the patient received any protocol treatment, all data (except biospecimens) up until the point of confirmation of ineligibility must be submitted. Event monitoring will be required per Section 18.0 of the protocol.

- If the patient never received any protocol treatment, on-study material (except biospecimens) and the End of Active Treatment/Cancel Notification Form must be submitted. No further data submission is necessary.

13.6 A patient who withdraws consent before any study treatment is given. On-study material (except biospecimens) and the End of Active Treatment/Cancel Notification Form must be submitted. No further data submission is necessary.

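### Response is defined over two different patient sets (1.9c11 and 16.1), and with no all-treated safety set a treated patient later ruled ineligible is by implication left out of the final toxicity proportions

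*Combined protocol and SAP*

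**What the plan says.** Three places bear on who is counted.

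- **Section 1.9c11** takes the proportion with confirmed response, with a 90% confidence interval, "among all the patients enrolled on this trial".
- **Section 16.1** states "This pilot study will enroll 10 patients" and then: "All patients meeting the eligibility criteria who have signed a consent form and have begun treatment will be evaluable". The sentence goes on to cover all clinical endpoints. The same section says that, with no responses in ten, the "upper bound of a one-sided 95% confidence interval for the tumor response rate would be 25.9"%.
- **Section 16.31** asks for the proportion of patients with a severe level of each toxicity and names no denominator. Section 16.21 likewise speaks only of a percentage of patients.

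Safety stands beside anti-tumor activity in the primary goal (2.1), and 1.9c12 labels it a clinical endpoint. Section 13.5 makes a patient ineligible if any single criterion was unmet at registration, even when this is discovered afterwards. It keeps part of the data: "If the patient received any protocol treatment, all data (except biospecimens) up until the point of confirmation of ineligibility must be submitted". Event monitoring follows. Section 13.3 lists ineligibility among the reasons to end protocol therapy.

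On eligibility itself, 3.17 has two sentences on renal function. For patients with creatinine above 1.5 x ULN, "Measured or calculated (per institutional standard) creatinine clearance is acceptable" at 60 mL/min or more. Then: "Calculated creatinine clearance can be used in place of creatinine or CrCl and must be" at least 45 mL/min. The albumin minimum is 2.5, in mg/dL.

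**The concern.** The sets in 1.9c11 and 16.1 coincide only if every registered patient starts treatment and none is later found ineligible. The protocol provides for both exceptions (13.5 and 13.6). When either occurs, the two sections give different response rates and intervals, and nothing says which is primary.

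The safety side matters more. A safety summary normally rests on exposure: a patient who received the drugs and had a severe event is informative about toxicity whether or not a laboratory value at entry met its limit. Here the only stated analysis set requires eligibility, and 16.31 does not override it. Section 13.5 sets no time limit on finding ineligibility, so in an open single-arm trial the finding may come after response or toxicity is known. Excluding patients on that basis can bias either result in either direction. With ten patients, one exclusion is visible in the reported figures.

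**Working it through.** **1. Who falls in which set**

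| Patient | 1.9c11 (enrolled) | 16.1 (eligible, consented, treated) |
|---|---|---|
| Eligible and treated | in | in |
| Registered, never treated | in | out |
| Treated, later ruled ineligible | in | out, by implication |

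No other section defines a safety set, so the third row also applies to 16.31.

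**2. The plan's own figure.** With zero events in n patients, the exact one-sided 95% upper bound is 1 - 0.05^(1/n). For n = 10 it is 1 - 0.05^(0.1) = 0.2589, or 25.9%, as stated. As a check, (1 - 0.259)^10 = 0.0499. It is also the upper limit of the exact two-sided 90% interval for 0/10, so it agrees with the interval in 1.9c11. The figure needs all ten patients in the denominator.

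**3. The same bound after exclusions** (the number excluded is an assumption)

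- n = 9: 1 - 0.05^(1/9) = 28.3%
- n = 8: 1 - 0.05^(1/8) = 31.2%
- n = 7: 1 - 0.05^(1/7) = 34.8%

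**4. Response with some responders** (illustrative counts, one non-responder excluded, exact 90% intervals)

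- 3/10 = 30% (8.7% to 60.7%) becomes 3/9 = 33% (9.8% to 65.5%)
- 4/10 = 40% (15.0% to 69.6%) becomes 4/9 = 44% (16.9% to 74.9%)

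**5. Severe toxicity** (illustrative counts, exact 90% intervals)

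- The excluded patient is the only one with an event: 1/10 = 10% (0.5% to 39.4%) becomes 0/9 = 0% (0% to 28.3%)
- The excluded patient is one of two with an event: 2/10 = 20% becomes 1/9 = 11%
- The excluded patient had no event: 1/10 = 10% becomes 1/9 = 11%

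For scale, 1.9c12 expects serious events in about 10-13% of patients, which is 10 x 0.10 = 1.0 to 10 x 0.13 = 1.3 patients. Serious is not the same as severe, as 10.1 notes, so this shows only that counts of about one are realistic.

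**6. What 13.5 preserves.** The first scan is at about week 12 and later ones every 12 weeks (11.1). Section 16.21 requires response at two assessments separated by 12 weeks or more. The earliest confirmed response is therefore at about week 12 + 12 = 24. A patient ruled ineligible before then would not have a confirmed response in the data that 13.5 requires.

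**7. Section 3.17.** Take creatinine above 1.5 x ULN and a calculated clearance of 45-59 mL/min. The first sentence rejects the value and the second accepts it. With creatinine at or below 1.5 x ULN the main criterion is met and the 60 mL/min sentence does not apply. For albumin, 2.5 mg/dL / 1000 = 0.0025 g/dL, a level that in practice excludes nobody.

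**The case against.** The strongest reply is that 16.1 says who is evaluable and never says that ineligible patients' toxicity is dropped. That is right: the exclusion is an inference, drawn because 16.31 has no denominator and no other set exists.

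A reader might go further and infer that such a patient's toxicity disappears from the trial. The documents do not support that. Serious events are reported under 10.4, routine adverse events under 10.6, and data up to confirmation of ineligibility under 13.5. The 16.61 rule counts enrolled patients, so a related grade 4 event still counts toward closing enrollment. Only the final summary is affected.

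A reader might also take 16.61 as a third, conflicting analysis population. It is a monitoring trigger, and its wider count is protective.

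Late ineligibility may be uncommon: eligibility is verified before registration is accepted (6.4), treatment begins at one site (6.9a), and 13.5 judges status as of registration. This stands as a limit on likelihood. It does not remove the gap, because 13.3 and 13.5 themselves provide for the case.

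The response effect is small next to intervals this wide, in a pilot with no efficacy threshold. That also stands.

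Finally, one might infer from 3.17 that eligibility, and so the 16.1 set, cannot be determined. That goes too far. The clearance conflict is confined to the band and condition in step 7. The albumin limit can be applied literally, and since it screens out nobody it cannot move a denominator.

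**Conclusion.** The point holds in this form. Sections 1.9c11 and 16.1 name different response denominators, and the plan has no safety set based on exposure. As written, 16.1 by implication omits a treated-but-ineligible patient from the final toxicity proportions, which belong to the primary goal.

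The 25.9% calculation is correct; what is unsettled is the population it will apply to. On an assumed one or two exclusions the zero-response bound moves to 28.3% or 31.2%. The toxicity effect ranges from about one percentage point (1/10 to 1/9) to loss of the only observed event (1/10 to 0/9). The larger effect requires that the excluded patient be the one with the event. The documents give no ineligibility rate, so these figures show sensitivity and are not forecasts.

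The 3.17 wording is a separate minor item. The clearance conflict can affect who counts as eligible in a narrow band; the albumin limit cannot.

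**What to change.** - **16.1 and 16.31:** define the safety set as every patient who received any dose of either study drug, whether or not later found ineligible, and use it for all toxicity proportions.
- **1.9c11 and 16.1:** name one response set in both places. A workable choice is all registered patients who began treatment, with no confirmed response counted as non-response. Report the eligible-only result as a sensitivity analysis.
- **16.61:** leave the trigger on its broad count.
- **13.5 and 16.1:** state how adverse events and response are handled after ineligibility is confirmed, since full data submission ends there.
- **3.17 (separate, minor):** the sponsor should reconcile the two clearance sentences and confirm the albumin unit. This review does not say which limit is right.

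The cost is a few sentences. If adverse events or scans are wanted beyond the point where 13.5 now stops, there is also some added data collection. The downside is dilution of response: an ineligible patient taken off treatment early counts as a non-responder, so, for example, 4/9 (44%) is reported as 4/10 (40%). The eligible-only sensitivity analysis shows how much this matters.
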